# 9.11 Risks of muscle strength testing

There is minimal medical risk or discomfort for the muscle strength testing.

# 9.12 Risks of activity monitoring and fatigue diary

There is minimal medical risk or discomfort from the physical activity monitoring and recording fatigue levels in a diary.

## 9.13 Risks of nutritional assessment and metabolic diet

There is minimal medical risk or discomfort from the nutritional assessments and maintaining a metabolic diet.

## 9.14 Risks of saliva collection

There is minimal medical risk or discomfort for providing saliva samples.

## 9.15 Risks of buccal swab collection

There is minimal medical risk or discomfort for providing buccal swabs.

## 9.16 Risks of stool sample collection

There is minimal medical risk or discomfort from stool sample collection.

## 9.17 Risks of Holter monitoring

There is minimal medical risk or discomfort from the Holter monitoring.

## 9.18 Risks of LP

Participants may have a brief pain or tingling sensation in their legs during the lumbar puncture if the needle brushes against a nerve. Participants will be instructed to let the study team member know immediately and the needle will be adjusted. Some people get a mild backache at the site of needle insertion. About one-third of people have a headache for a few days after a lumbar puncture. Usually the headache is not severe and improves without treatment other than a mild pain reliever. Headaches lasting longer than 7 days develop with one in 50 to 200 lumbar punctures and usually improve gradually over 2 weeks. In rare cases, headaches persist longer. Prolonged headaches may be due to persistent leakage of CSF from the area of the lumbar puncture. If the headache is prolonged, participants may get a blood patch. Collecting ~20 ml of CSF per procedure represents negligible risk (Evans, et al. 2000). In adults the rate of CSF synthesis is approximately 21.5 ml/hour, or approximately 500 ml/24 hours, which represents roughly 4 times the total volume of CSF in adult patients. Therefore, the maximum volume of 24

ml of CSF that would be collected will be replenished in its entirety within approximately 1-1.5 hours after collection.

# 9.19 Risks of sedation for LP

Sedation with low-dose benzodiazepines is associated with a small risk of respiratory depression and an even smaller risk of cardiac arrhythmias. More common risks are: sleepiness, dizziness, weakness, unsteadiness, hallucinations, confusion, and rarely an allergic reaction causing rash, hives, or swelling.

# 9.20 Risks of fluoroscopic-guided LP

Fluoroscopy may be used during LP to facilitate placement of the needle into the subarachnoid space. Participants who undergo fluoroscopy will be exposed to radiation in the amount of 23 mrem, (or 46 mrem for two procedures) which is within the safety limit of 5 rem (5000 mrem) per year set by the NIH Radiation Safety Committee for adult research subjects. If participants would like more information about radiation and examples of exposure levels from other sources, they will be provided with the flyer, "An Introduction to Radiation for NIH Research Subjects."

# 9.21 Risks of autonomic testing

Dynamic heart rate and blood pressure monitoring during respiratory, positional and valsalva maneuvers: The blood pressure monitoring consists of blood pressure sensor placed on the finger, this has a squeezing sensation which can be slightly uncomfortable. The heart rate monitor, similar to a standard EKG recording, will have three surface leads placed on the chest and torso area to noninvasively monitor heart rate. The chest expansion monitor will consist of a strap wrapped around the low chest to record the breathing pattern. It can be cumbersome but otherwise is painless. The testing maneuvers of deep breathing, Valsalva or tilt test may cause lightheadedness, syncope, and arrhythmias in some people. Though rhythm disturbances have been noted, the most common being extra systoles, the dysrhythmias appear to resolve without medical intervention. The Valsalva maneuver can also cause an increase in intraocular and intracranial pressure but there has not been any reported complications related to intraocular hemorrhage or lens displacement.

# 9.22 Risks of cytapheresis

Cytapheresis can cause lightheadedness or fainting. Some people have tingling in the fingers or around the mouth. The citrate blood thinner used to prevent blood clots during apheresis can cause mild muscle cramps. We will slow down the blood flow and/or administer calcium carbonate (Tums or similar oral formulation) if participants complain of symptoms. If the symptoms do not go away, we will stop the cytapheresis.

## 9.23 Risks of immune cell blood draw

Participants may have some discomfort and bruising at the site of needle entry. There is a very small risk of fainting. Infection in the area of the needle insertion is rare.

## 9.24 Risks of medication washout

There is a more than minimal risk for the planned tapering off of medications that potentially interfere with brain excitability. Participants may experience an increase in

their typical symptoms or experience symptoms related to the cessation of medications. Patients may decide to discontinue with the medication taper if it is too difficult for them to tolerate.

# 9.25 Risks of metabolic chamber

Besides inconveniences that can reasonably be expected as a result of spending an extensive time (overnight) in the live-in room calorimeter, there is no risk to subjects' physical health. Claustrophobia is an exclusionary criterion. All subjects will be given an opportunity to experience the metabolic chamber prior to enrollment in the study. Risks of dual energy x-ray absorptiometry

# 9.26 Risks of DEXA

For each scan (around 12 minutes), the amount of radiation (effective dose) during the DEXA scan is less than one mrem to the whole body. This radiation exposure is below the guideline of 5000 mrem per year allowed for research subjects by the NIH Radiation Safety Committee The use of the DEXA scan apparatus may cause some minimal discomfort in claustrophobic subjects and may cause some minimal back pain in a small minority of the individuals.

**9.27** Risks of resting energy expenditure measurements by ventilated hood The use of the clear plastic ventilation hood may cause some minimal discomfort in claustrophobic subjects

# 9.28 Risks of peak exercise testing

Exercise testing may be risky for participants with cardiac disease so participants with known cardiac disease will be excluded from the study. Participants who do not have known cardiac disease are believed to be at low risk from exercise tests using a bike or a treadmill. The major risk of this type of exercise in general is that someone may have unknown or asymptomatic cardiac disease. Even though participants will be examined before the study to try to detect the presence of cardiac disease, it is possible to have unknown cardiac disease that can lead to angina, arrhythmia, or death during the test. The risk of death for healthy adults who undergo maximum exercise is between 0 and 3 deaths/100,000 tests. During the test, the participant's heart rhythm will be constantly monitored by the study team. A participant will stop the test at the earliest sign of cardiac problems whether those signs are from the monitor or based on symptoms. Other risks of exercise include the risk of falls while using the treadmill or short-term myalgia or arthralgia caused by exercising that could last several days. Participants will be instructed to tell the study team if myalgia or arthralgia becomes bothersome as these may be treated with as needed mild pain relievers.

# 9.29 Risks of Qualitative Interviews

Answering questions about one's illness could elicit negative feelings or emotions. Interviewers will be cognizant of this during interviewing and make every attempt to put the patient at ease and remind respondents that they can decline to answer questions and/or terminate the interview.

# 9.30 Blood measurements before and after CPET

There is minimal medical risk from blood sampling from the IV line.

# 9.31 Risks of Effort-Expenditure for Rewards Task

This computer test of effort expenditure for perceived reward is similar to other computer based neuropsychological tests. This task is not harmful but may be frustrating or stressful. Participants may stop this task or withdraw from the study at any time and for any reason.

# 9.32 Risks of TMS

TMS may cause strong contractions of scalp muscles leading to discomfort or a headache. If participants find TMS too uncomfortable, they may stop it any time. Headaches usually go away by themselves or with nonprescription medication. The noise of the TMS magnet can damage hearing, so participants will be fitted with earplugs which must be worn during TMS. TMS can interfere with implanted medical devices. Participants will not be able to have TMS if they have a pacemaker, implanted pump, a stimulator (such as a cochlear implant) or metal objects inside the eye or skull.

Risk of skin irritation at the site of the EMG electrode may be minimal in some subjects. There are no medical risks associated with surface EMG.

# 9.33 Risks of sleep electroencephalogram

There is no known risk concerning the EEG technique itself. The electrode cap can be uncomfortably tight. There may be mild irritation of the skin and scalp from the mild abrasion needed to assure good contact or from the collodion, paste, or gels used.

## 9.34 Risks of Medical, Psychiatric, Sleep Service and Rehabilitation Consultation

There is minimal medical risk or discomfort from medical, psychiatric, sleep, and rehabilitation consultation.

# 9.35 Risks of genetic testing

Genetic testing can provide information about how illness is passed on within a family. This knowledge may affect participants' emotional wellbeing. They might feel differently about their life if they learned that they or their children were at increased risk of a disease, especially if there were no treatments. Their children, brothers or sisters may find out that they are at risk for health problems because of information found out about the participants, which might affect the participants' relationships with family members. Other family members may also be affected by uncovering risks they have but did not want to know about. This information can cause stress, anxiety, or depression.

Some genetic testing can also determine if people are directly related. These tests sometimes show that people were adopted or that their biological parent is someone other than their legal parent. If these facts were not known previously, they could be troubling. Genetic counseling is available at the NIH to help participants understand the nature and implications of genetic findings.

Because of the emotional risk, some participants do not want to know the results of genetic testing. It is our policy to not disclose the results of genetic testing unless it may have direct medical or reproductive implications for participants or the participants'

families. Any genetic results disclosed to participants will be done in the context of genetic counseling.

Results of genetic testing obtained at NIH are often preliminary and difficult to interpret because the testing is being done for research purposes only and the laboratories are not CLIA-certified. If a reportable genetic change is noted on a non—CLIA genetic test, the protocol will cover the costs of confirming the result using a CLIA genetic test.

Genetic information will be kept confidential to the extent possible. The results of genetic testing will be kept in a locked and secured manner at the NIH.

Problems, such as with insurance or employment discrimination, may occur if they disclose information about themselves or agree to have their research records released. We will not release any information about participants to any physician, insurance company or employer unless they sign a document allowing release of the information.

# 9.36 Risks of Skin Biopsies

The skin punch-biopsies have potential risks including infection, bleeding, pain, and potential scarring.

## 9.37 Risks of Muscle Biopsy

The muscle punch-biopsy procedure has potential risks including infection, bleeding, pain, and post-procedure anesthesia or paresthesia if a cutaneous nerve is damaged. The risk of these events is minimized by having the procedure performed only by experienced physicians under sterile conditions with adequate local anesthesia.

# 10 Subject Safety Monitoring

Study personnel, overseen by the PI, will closely monitor participant safety during study procedures. If, during the course of interviewing, assessment procedures and the research procedures, study staff identifies a condition that should require immediate clinical intervention, all necessary steps will be taken. Parameters to be monitored for safety reasons include level of consciousness. All MRI scans will be monitored in accordance with NIH Clinical Center policies. Toxicity will be assessed according to the most recent version of the NCI Common Terminology Criteria for Adverse Events (CTCAE). Participants will be removed from the study if they are unable to cooperate with the study procedures, if a medical exclusionary condition develops, or if the PI judges discontinuation to be in the participant's best medical interest.

## **11 Outcome Measures:**

The primary purpose of this protocol is to perform exploratory analysis of collected samples for the generation of new hypotheses regarding ME/CFS. The types of analyses to be performed will be wide ranging. Planned areas of focus include:

1. Characterization of the immune system and inflammatory signaling in collected samples at baseline and following maximal exercise exertion.

2. Characterization of the pattern of microbiome in collected samples at baseline and following maximal exercise exertion.

3. Characterization of bioenergetics, autonomic, and metabolic function in collected samples at baseline and following maximal exercise exertion.

4. Characterization of physical and cognitive fatigue using functional magnetic resonance imaging and transcranial magnetic stimulation at baseline and following maximal exercise exertion.

5. Characterization of neurocognition at baseline and following maximal exercise exertion.

## **12** Statistical Analysis

# 12.1 Analysis of data/ study outcomes

The studies performed under this protocol are exploratory. Quantitative research data will be acquired and logged into a database. The PI or designated investigator will monitor data integrity. Because a variety of types of data will be obtained in the study, the statistical methods most appropriate for the nature of the data will be used. Some of the relevant statistical approaches are as follows:

We are primarily interested in evaluating whether various types of data obtained are significantly different between the three groups as measured in cross-section during the phenotyping visit as well as between HV and PI-ME/CFS groups before and after an exercise stress. Each of these groups will be characterized using standard descriptive statistical methods.

As noted in Section 4.5, ME/CFS participants that are found no to meet the strict inclusion/exclusion of this study all have been diagnosed with ME/CFS by health providers and represent ME/CFS in the community. HVs and COVID-19 HVs that do not have fatigue or PEM may also be found to medical issues or other findings that would exclude them from meeting the strict inclusion/exclusion criteria of being healthy, but still represent a non-fatigue comparator to ME/CFS patients. The primary focus of the analyses detailed below will be between adjudicated ME/CFS participants and HVs and COVID-19 HVs that meet all inclusion/exclusion criteria. If the result of a primary analysis is positive, a secondary analysis will be repeated using all of participants. Findings that remain robust even when less stringent inclusion/exclusion criteria are used suggest that they are more likely to be replicable in community cohorts and perhaps worthy of further exploration.

For each continuous-scale outcome, repeated measures analysis of variance (ANOVA) will be used to test whether there are significant differences in cross-sectional measurements as well as in the pre and post measurements among two groups by using F tests. These initial tests will be performed using the adjudicated PI-ME/CFS group (i.e. participants determined to have PI-ME/CFS by the protocol's adjudication process) compared to HV and COVID-19 HV participants meeting all inclusion and exclusion criteria. The cross-sectional analyses may then be repeated using all HV and COVID-19 HV participants that did not report substantial clinical fatigue as noted above.

If the overall multivariate test is significant, we will follow up with several post-hoc tests. Specifically, we will first conduct multivariate tests to compare the adjudicated PI-ME/CFS group (i.e. participants determined to have PI-ME/CFS by the protocol's adjudication process) vs the other two control groups, and the PI-ME/CFS group vs each of the two control groups. These analyses will initially performed using only HV and COVID-19 HV participants meeting all inclusion and exclusion criteria. As noted above, for analyses that are statistically significant, the analysis will be repeated using all HV and COVID-19 HV participants that did not report substantial clinical fatigue to determine if the results remain statistically significant when less stringent inclusion/exclusion criteria are applied.

Second, univariate ANOVA will be used for both cross-sectional measurements and pre and post exercise measurements separately to identify differences among groups. A
similar univariate analysis will be conducted for the measurements of change from pre- to post exercise using the univariate ANOVA.

Additionally, descriptive statistics will be used to characterize the entire group of ME/CFS participants that completed the phenotyping evaluation regardless of adjudication. Comparisons will be made between the adjudicated PI-ME/CFS group and the phenotyping ME/CFS group. If there is no significant difference between the above two groups, it is not necessary to compare a ME/CFS group to our two control groups. Where statistically appropriate, the ANOVA methods described above will be used to compare the ME/CFS group with the two control groups.

Statistical approaches such as chi-square tests and multinomial logistic regression models will be used to examine the group differences for categorical outcomes.

A level of significance is set at 0.05. Multiple comparison test procedures such as Bonferroni and Dunnett's methods will be used to examine the differences in each outcome measure among groups.

The primary MRI imaging aim is to test whether PI-ME/CFS group has significantly different connectivity patterns compared to the HV control group.

To this end, functional MRI measures will be taken at three conditions: 1) performing a force task, 2) performing a cognitive task, to define a network of interest, and 3) at rest to compute functional connectivity. At each condition, fMRI will be measured at two time points: pre exercise (preEx) and post exercise (postEx).

We will use a multivariate regression model where the response variable is connectivity strength among regions of interest pre- and post- exercise. Predictors include group status and fatigue scores.

Region of interest for the connectivity analysis will be defined based on tasks 1) and 2). For this, data will be pre-processed with standard techniques using AFNI. Imaging quality assurance will be performed (i.e. motion correction parameters). We will fit a multivariate regression model to detect the differences in activity patterns of each task. Behavior and scales of fatigue will be entered as covariates.

Significance of the results will be set at p = 0.05 corrected for multiple comparisons for all analyses.

Lastly, we will conduct receiver operating characteristic (ROC) analysis for selected markers that are potentially important, which will be identified by exploratory analysis and several statistical approaches mentioned above. We will evaluate the accuracy of each marker for its ability to classify subjects in the PI-ME/CFS group from those in the HV control group. For example, if MRI imaging measurements are significantly different among groups, next, we will calculate the nonparametric area under the ROC curve (AUC) for each imaging marker and its 95% confidence interval.

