### 3 Subjects

#### 3.1 Description of study populations

Up to 346 persons will be enrolled as part of this protocol. Up to 150 persons aged 18-60 will be part of 3 study groups: 50 PI-ME/CFS patients, 50 healthy volunteers (HV), and 50 asymptomatic and healthy persons with a documented history of COVID-19 infection (COVID-19 HV). The study has a target of completing all study procedures on 20 enrolled participants in each group. Any participant who withdraws prior to the completion of the study procedures may be replaced. Up to an additional 176 persons reporting a community diagnosis of ME/CFS will be enrolled into focus groups to discuss the experience of post-exertional malaise. Up to an additional 10 healthy volunteers and 10 ME/CFS participants may be enrolled to refine the protocol's electrophysiological and neuroimaging techniques.

The PI-ME/CFS group will consist of persons reporting persistent and severe fatigue and post-exertional malaise as the consequence of an acute infection without a prior history of medical or psychiatric illness. PI-ME/CFS pre-screening will review medical records and will seek to identify persons with a community diagnosis of ME/CFS that started within 6 months after an infectious illness that do not have other potential medical causes for their symptoms.

Potential PI-ME/CFS participants that meet inclusion and exclusion criteria for a *phenotyping visit* on pre-screening will be invited to participate and undergo a full week of medical interviews and research measurements. This collected information will be used in a *case adjudication process* to determine if a participant meets criterion to return for a separate *exercise stress* visit. *Exercise stress* visit participants are required to meet more stringent inclusion and exclusion criteria to best ensure that participants have ME/CFS that started after an infection, meet published diagnostic criteria, have an appropriate level of symptom severity and physical function to undergo the protocol's exercise stress procedure, and do not have exclusionary co-morbid health issues. This process has necessitated two sets of inclusion criteria for PI-ME/CFS participants: phenotyping criteria (Sections 3.2.2 and 3.3.2) and exercise stress visit criteria (Sections 3.2.3 and 3.3.3).

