Participants in this study will undergo a great number of procedures in a relatively short period of time. All of the procedures that are to be performed in this study are standard research measurements, with well-defined risks and discomforts. No particular measurement or procedure is exceedingly burdensome, however the cumulative burden of undergoing all of these procedures is significant. This burden is a reasonable one, as it is the intent of this study to induce fatigue and PEM in its participants. However, PI-ME/CFS patients are defined by their vulnerability to exhaustion. It is probable that some participants will be unable complete the entire study. Some participants may also be so exhausted by the study that they may require some time to recover prior to travelling home. Thus, the study team will be solicitous of the participants in regard to their comfort and flexible to provide for their needs.

This 'Phase I' study will analyze the collected data in an exploratory manner. The goal of these analyses is to identify physiological alterations for the purpose of hypothesis generation. A broad array of laboratory methods that query different aspects of human physiology will be performed on collected samples. The protocol is looking for positive results that would generate testable hypotheses and for negative results that will provide a sense of the biological measurements and physiological mechanisms where large differences are unlikely to be seen with future study. De-identified data and biological samples will be shared with a wide range of collaborators, both within NIH and across the world. A larger 'Phase II' study is planned that will use these results to determine potential mechanisms for intervention and estimate effect sizes for larger clinical and interventional studies.

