# 12.2 Power analysis

The accrual ceiling for participants in the phenotyping and exercise stress arms of this study is 150 participants (50 per group) and dropouts will be replaced. The sample sizes were chosen based on convenience and equals about 1-2 participants per week. This is a phase I pilot study intended to explore a variety of clinical and biological data from the three different groups. For neuroimaging studies of somatosensory stimulation, it is estimated to require 12 subjects to achieve 80% power at the threshold of 0.05 to determine differences at the single voxel level for typical activations. The proposed sample size of 20 participants per group should be adequate for distinguishing group differences in fMRI activity during the proposed fatiguing tasks. The study is exploratory and its results will be used to estimate effect sizes to design a larger clinical study.

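### Section 12.1 has no method for incomplete Visit 2 data: if dropout after exercise follows PEM severity and only completers are analysed, the PI-ME/CFS versus HV difference may be understated

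*Combined protocol and SAP*

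**What the plan says.** - **Method.** Section 12.1 states for continuous outcomes that "repeated measures analysis of variance (ANOVA) will be used to test whether there are significant differences in cross-sectional measurements"; the same sentence extends this to pre- and post-exercise measurements, using F tests. If the overall multivariate test is significant, follow-up tests come next. They include separate univariate ANOVAs before and after exercise, and then: "similar univariate analysis will be conducted for the measurements of change from pre- to post exercise using the univariate ANOVA".
- **Latitude.** The section opens by saying that "the statistical methods most appropriate for the nature of the data will be used" and presents its list as some of the relevant approaches.
- **Schedule.** Sections 4.6.6 and 4.6.14 set six time points for symptom scales and blood: one before CPET and five after, the last at 68-76 hours.
- **Non-completion.** Section 4.1 describes a heavy cumulative burden, says that the study intends to induce fatigue and PEM, and adds: "It is probable that some participants will be unable complete the entire study". Section 10 removes participants who cannot cooperate with the procedures.
- **Replacement.** Section 3.1: "The study has a target of completing all study procedures on 20 enrolled participants in each group". It continues: "Any participant who withdraws prior to the completion of the study procedures may be replaced". Section 12.2 is firmer: "150 participants (50 per group) and dropouts will be replaced".
- **Not stated.** Section 12 gives no missing-data method, no analysis-set rule for someone who withdraws during Visit 2, and no sensitivity analysis. No section says whether a replaced participant's data are kept.

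**The concern.** Classical repeated-measures ANOVA needs a full set of measurements from each participant, and so does a multivariate test on the vector of time points. Where the plan is silent, that default applies. The protocol itself connects non-completion with exhaustion, which is close to the phenomenon being measured and is expected mainly in one group. Section 4.6 expects PEM within 24-48 hours, and section 4.6.13 puts its peak at 24-72 hours. A participant lost after onset would therefore miss the most informative assessments.

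At stake are estimates rather than a confirmatory test. Exploring PEM is the secondary objective. Sections 4.1 and 12.2 intend the results to supply effect sizes for a larger study, and section 4.1 also wants negative results to show where large differences are unlikely. Attenuated estimates would harm both uses.

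**Working it through.** **The plan's own figure.** The only power figure, in section 12.2, is 12 subjects for 80% power at 0.05 at single-voxel level. No effect size is given, so it cannot be reproduced forwards. Solved backwards with the two-sided normal formula, it implies a one-sample standardised effect of (1.960 + 0.842)/√12 = 0.81. It says nothing about dropout or missing data. Every dropout rate below is an assumption.

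**Step 1: complete cases.** With independent loss p at each of k time points, the complete fraction is (1 − p)^k.
- Six points: 0.95^6 = 0.735 and 0.90^6 = 0.531.
- Only one pre and one post value: 0.95^2 = 0.903 and 0.90^2 = 0.810.

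This shows the loss of data, not bias. Independent misses are not the mechanism of concern, and one of the six points precedes CPET.

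**Step 2: would the completer target reveal a problem?** Enrolment needed for 20 completers is 20/(1 − d), rounded up. For d = 10%, 20%, 30% and 40% that is 23, 25, 29 and 34. The ceiling of 50 allows 1 − 20/50 = 60% non-completion from all causes, including patients not passed at adjudication. Reaching 20 completers is therefore no evidence that loss was small or unselective.

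**Step 3: an extreme bound.** Suppose PEM change is normally distributed and exactly the most severe fraction d leaves. The completer mean then shifts by −φ(z)/(1 − d) standard deviations, where z is the (1 − d) normal quantile. For d = 10%, 20%, 30% and 40% this gives −0.19, −0.35, −0.50 and −0.64 SD. If dropout is unrelated to severity, the shift is 0.

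**Step 4: less extreme mechanisms.** This is a simulation of 400,000 patients at six time points.
- Assumed mean profile: 0, 0.3, 0.5, 1, 1 and 0.8 SD.
- Individual response multiplier: mean 1, SD 0.8.
- Random-intercept share of the remaining variance: 0.6.
- Dropout: logistic, with slope 1 per SD of its driver in (b) to (d); those who leave are lost from 20-28 hours onwards.
- All-data estimate: predicts the missing 44-52 hour value from the first three time points, as a normal likelihood would.

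Relative error in the mean change from before CPET to 44-52 hours:

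| Dropout mechanism and estimate | 10% | 20% | 30% | 40% |
|---|---|---|---|---|
| (a) Unrelated to PEM, completers | −0.1% | +0.2% | 0.0% | +0.1% |
| (b) Follows PEM seen at 4-6 h, completers | −6.7% | −12.7% | −18.8% | −24.4% |
| (b) All observed data | 0.0% | 0.0% | −0.2% | −0.2% |
| (c) Follows PEM at 44-52 h, unseen in leavers, completers | −10.9% | −20.9% | −30.3% | −39.6% |
| (c) All observed data | −6.4% | −12.5% | −18.3% | −24.2% |
| (d) Mildest PEM leaves, completers | +11.0% | +20.9% | +30.3% | +40.0% |
| (d) All observed data | +6.5% | +12.5% | +18.4% | +24.5% |

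These errors concern the patient group. They carry over to the group difference in the same proportion only if healthy volunteers have no selective loss and no mean change.

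**Reading.** The sign depends on who leaves. Using all observed data removes the bias when dropout depends on what was already measured (b). It only reduces the bias when dropout depends on what was not measured (c, d).

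**The case against.** The strongest reply is that the plan nowhere restricts the analysis to participants with every time point. That is a property of the default method. Section 12.1 speaks of pre and post measurements, which may mean two levels rather than six. Separate ANOVAs at each point can use whoever was measured there, and a change score needs only a pair. The opening sentence on method, and section 12.3's statement that each analysis will suit its data, would both permit a mixed model. All of this stands as to wording. But the separate and change-score ANOVAs are follow-ups to a significant overall test, a change score still loses anyone without the chosen post-exercise value, and permission for a better method is not a commitment to it.

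A reader might also infer that the patients with the worst PEM will leave, so that PEM is certain to be understated. The documents do not support that. Section 4.1 says only that some participants may not finish the whole study. It gives no rate, does not place the loss after CPET and does not rank leavers by severity. Loss at Visit 1, adjudication or medication taper removes nobody with post-exercise data. After CPET, participants are inpatients observed for 72 hours, and stays can be extended (section 4.6), which may keep loss small. Some missing Visit 1 data were due to equipment or staffing (section 4.5).

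Nor does replacement delete data. It does harm only if withdrawn participants are then left out. The qualitative PEM interviews fall outside the ANOVA and are not affected by this point.

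**Conclusion.** The point holds in conditional form. The plan names a method that in its classical form discards incomplete participants, expects exhaustion-related non-completion, replaces withdrawals, and has no rule for incomplete Visit 2 data. If dropout after CPET follows PEM severity and only completers are analysed, the PI-ME/CFS versus HV post-exercise difference may be understated.

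The size cannot be taken from the documents. Under the assumptions above, completers understate the patients' mean change by about 7% to 24% at 10% to 40% dropout when loss follows PEM already observed. The error is nil when loss is unrelated to PEM, and it reverses if the mildest cases leave. A firm statement that PEM will be understated goes beyond the text. The change is still worth making: it is nearly free, and section 12.3 reports that an interim analysis of the ME/CFS and HV cohorts has already been initiated.

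**What to change.** In section 12.1, for quantitative Visit 2 outcomes:
1. Replace repeated-measures ANOVA with a likelihood-based mixed model with group, time, group × time and within-participant correlation. Use every observed time point from everyone who had CPET, including participants later replaced.
2. Report the time of, and reason for, each missed post-CPET assessment by group.
3. Add a delta-adjusted sensitivity analysis for data missing not at random, because the main model removes the bias only under missing at random.
4. Reconcile section 3.1, where withdrawals *may* be replaced, with section 12.2, where they *will* be, and state that a replaced participant's data stay in the analysis.

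The cost is SAP wording, slightly more analysis work, and reliance on missing at random in the main model.
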